9.4.2 ANALYSIS OF THE PRIMARY ENDPOINT(S)

Mixed-model RM-ANOVA will be used to estimate and compare the changes in the primary endpoint (ISI) and other patient-important outcomes (e.g., insomnia symptom severity, daytime sleepiness) between Somryst and mEUC. The RM-ANOVA model will include Group (Somryst versus mEUC), Time (baseline, post-intervention and 6-month follow-up), and the Group × Time interaction as fixed factors with an unstructured residuals covariance matrix. This will yield estimates of the within-group means and standard errors at each assessment. Specific interaction contrasts (e.g., Group × Pre-vs-Post Intervention) will be estimated to estimate the magnitude and test the statistical significance of the differential change in insomnia symptoms using the Wald χ^2 statistic. We will plot the mean insomnia scores across assessments, stratified by treatment group, to elucidate the nature of the interaction (i.e., whether Somryst resulted in significantly greater improvements [or lesser worsening] than mEUC). If, despite randomization, the two groups differ substantially (p<0.10 after stepdown Bonferroni correction) on one or more sociodemographic or clinical factors assessed at baseline, sensitivity analyses will be performed in which these factors are included as covariates in the RM-ANOVA, in order to rule out the possibility that the results from the primary analyses are attributable to group differences on these factors. The same analyses will be repeated to estimate and compare changes in the primary endpoint and secondary endpoints between Somryst and mEUC at 6-months.

Significance will be evaluated with a two-tailed p value of 0.05. To control for multiplicity, postintervention will be evaluated first and if significant timepoints post-intervention and 6-months followup will be evaluated. In addition, estimated marginal means \pm 95% confidence intervals will be calculated for each assessment point and Cohen's d will be used as an estimate of effect size for the change from baseline to each assessment point.

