9.4.3 ANALYSIS OF THE SECONDARY ENDPOINT(S)

For secondary endpoints, , we will follow Hochberg's step-up approach as outlined in Figure 2.

Figure 2. Decision structure for hypothesis testing of primary and secondary endpoints

Coupled with our primary hypothesis that CBT-I will result in improved ISI scores, a secondary hypothesis is that CBT-I will result in *greater improvement in* quality of life, as captured by the more general SF-12 that will be measured pre- and post-intervention in both the CBT-I and mEUC participants. We will use the validated method of Brazier et al. to calculate utilities (QALY penalties) from baseline and post-intervention SF-12 data by first mapping responses to the simpler SF-6D scale and then using a regression model to estimate single index scores.^{97, 98}_The cost-effectiveness analysis will compare incremental costs and quality-adjusted life years (QALYs) gained in the CBT-I arm compared with mEUC. The primary cost-effectiveness analysis will be from the payer's point of view (government, insurer, or health

18 May 2022

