Cost-effectiveness will be assessed based on the study observation period (9 weeks) in the main analysis, but micro- simulation analyses will simulate sustaining the insomnia prevention effects of CBT-I and EUC for years into the future, up to 10 years. Incremental cost-effectiveness ratios (ICERs) will be calculated as incremental change in costs divided by incremental change in QALYs comparing Somryst to mEUC).). ICERs will be assessed as follows (in 2021 U.S.): <50,000 per QALY gained will be considered cost-effective, \geq 50,000 and <150,000 of intermediate value, and \geq 150,000 of low value. Non-parametric bootstrapping with 1,000 random samples of all QALY and cost distributions

will be used to generate 95% uncertainty intervals for cost- effectiveness ratios.¹⁰⁰ Sensitivity analyses will test the robustness of the cost-effectiveness estimate to a range of inputs regarding intervention costs, productivity and quality of life losses related to chronic insomnia, size of quality of life improvement effect, and durability of intervention effect (ranging from one month to ten years). Cost-effectiveness analyses will be carried out and reported according to the Consolidated Health

Economic Evaluation Reporting Standards (CHEERS).¹⁰¹ Cost-effectiveness analyses will be carried out in TreeAgesoftware (TreeAge Inc., Williamstown, MA)

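### The cost-effectiveness verdict and its 95% interval rest on the ICER alone, with no rule for a QALY difference at or below zero; net benefit would close the gap at no cost

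*Combined protocol and SAP*

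**What the plan says.** Under Section 9.4.3 (Analysis of the Secondary Endpoints) the ICER is "calculated as incremental change in costs divided by incremental change in QALYs comparing Somryst to mEUC". It is graded in three bands, in 2021 U.S. currency, which I take to be dollars. The lowest band is "<50,000 per QALY gained will be considered cost-effective"; from 50,000 to below 150,000 is intermediate value, and 150,000 or more is low value.

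Uncertainty is attached to the same ratio: "Non-parametric bootstrapping with 1,000 random samples of all QALY and cost distributions" "will be used to generate 95% uncertainty intervals for cost- effectiveness ratios". The type of bootstrap interval is not stated.

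The horizon is short: "Cost-effectiveness will be assessed based on the study observation period (9 weeks) in the main analysis". Utilities are derived "from baseline and post-intervention SF-12 data by first mapping responses to the simpler SF-6D scale". The section also says that "Sensitivity analyses will test the robustness of the cost-effectiveness estimate to a range of inputs", including effect size and durability.

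The cost-effectiveness text has no rule for a negative ratio, for dominance, or for a QALY difference of zero or less. It names no net benefit, cost-effectiveness plane or acceptability curve. It also states no expected cost difference, utility difference or SD.

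**The concern.** A ratio of two differences can be ranked only while the denominator is positive. Once the QALY difference can be zero or negative, one ICER value can describe opposite situations. A negative ratio arises both when Somryst is cheaper and better and when it is costlier and worse. A large positive ratio arises both when Somryst costs a lot for a small gain and when it saves a lot for a small loss. Cut-offs on the ratio cannot separate these cases, and an interval built from replicates on both sides of zero pools them.

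Determining cost-effectiveness is a stated purpose of the RCT (Section 1.3), and the Section 3 table places economic analysis in Aim 2. The band label is the headline result of that aim. The rule must therefore also work when the quality-of-life effect is small or absent, and that is where it fails.

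**Working it through.** **1. The plan's own figure.** The only design figure that can be reproduced is the power statement in Section 9.2: 3-point ISI difference, SD of change 6.0, 170 patients with follow-up. With 85 per arm and two-sided 0.05 (Section 9.4.2: "Significance will be evaluated with a two-tailed p value of 0.05"), power is 0.903, which matches the stated 90%. I carry 85 per arm forward.

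**2. The cut-offs applied numerically.** Let dC and dQ be the cost and QALY differences, Somryst minus mEUC. ICER = dC/dQ. Incremental net benefit at 50,000 is INB = 50,000 × dQ − dC. The pairs below are illustrative.

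| dC | dQ | ICER | Band if read numerically | INB at 50,000 |
|---|---|---|---|---|
| +900 | −0.002 | −450,000 | cost-effective | −100 − 900 = −1,000 |
| −900 | −0.002 | +450,000 | low value | −100 + 900 = +800 |
| −50 | −0.002 | +25,000 | cost-effective | −100 + 50 = −50 |

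All three labels disagree with the sign of net benefit. This step needs no assumption about the trial's economics.

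**3. How often the QALY difference is at or below zero.** The documents give no inputs, so these are assumptions: 85 per arm, utility SD s = 0.10 to 0.15 at each visit, baseline to 9-week correlation r = 0.6, true 9-week utility gain du = 0.02 to 0.05, linear change over 9 weeks. Then dQ = 0.5 × (9/52) × du, which is 0.0017 to 0.0043 QALY.

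The factor 0.5 × 9/52 multiplies both the difference and its standard error, so it cancels. On the utility scale:

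- unadjusted area under the curve: SE = s × √(2 + 2r) × √(2/85), which is 0.0274 for s = 0.10 and 0.0412 for s = 0.15;
- change from baseline: SE = s × √(2 − 2r) × √(2/85), which is 0.0137 and 0.0206.

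P(estimate ≤ 0) = Φ(−du/SE). P(95% interval includes 0) = Φ(1.96 − du/SE) − Φ(−1.96 − du/SE). Ranges are over s.

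| du | Unadjusted: P(≤ 0) | Unadjusted: interval includes 0 | Change: P(≤ 0) | Change: interval includes 0 |
|---|---|---|---|---|
| 0.02 | 23-31% | 89-92% | 7-17% | 69-84% |
| 0.03 | 14-23% | 81-89% | 1-7% | 41-69% |
| 0.05 | 3-11% | 55-77% | 0-1% | 5-32% |

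At du = 0, P(≤ 0) is 50% on either basis.

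**4. Simulation of the rule.** Further assumptions: SD of utility change 0.10, cost difference $300 or $900, cost SD $1,000, 85 per arm; 600 trials per scenario, 1,000 bootstrap samples each, percentile limits.

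| du | Numerical label 'cost-effective' with negative INB | Trials with more than 2.5% of replicates at dQ ≤ 0 |
|---|---|---|
| 0 | 49-52% | 98% |
| 0.01 | 25-26% | 89-91% |
| 0.02 | 11% | 72-75% |
| 0.03 | 4% | 51% |
| 0.05 | 0% | 10-12% |

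Bootstrap intervals for INB covered the true value in 93-97% of trials in every scenario, including du = 0, where the true ICER does not exist.

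**The case against.** The strongest reply is that the lowest band is worded per QALY gained, so a costlier and worse Somryst has nothing to compare with 50,000. That stands. A reader might infer that the plan declares a dominated Somryst cost-effective, but the text does not say so. What remains is that the rule gives no verdict for QALY losses and misleads only if the numbers are applied mechanically.

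Other stronger readings also fail:

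- **The 9-week horizon makes a sign change likely.** The horizon shrinks effect and error together. The chance depends on the utility effect, its SD and whether QALYs are adjusted for baseline, none of which the cost-effectiveness text states.
- **The intervals are percentile intervals.** The type is not given. The difficulty applies to any interval on a ratio whose denominator straddles zero.
- **The intervals undercover.** In the simulation, percentile limits for the ratio covered the true ratio in 96-98% of trials when du was positive. The fault is one of interpretation.
- **Costs and QALYs are resampled separately.** The wording is ambiguous on this and does not say so.
- **The share of replicates below 50,000 would mislead.** The plan does not propose to report that share.

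It is also fair to say that this is a secondary analysis. The planned sensitivity analyses do not fill the gap, because they vary inputs and leave the decision rule unchanged.

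**Conclusion.** The point holds as a gap in the decision rule and a poor choice of quantity for the interval. The missing rule is visible in the text, and the misordering in step 2 is plain arithmetic.

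How often it would matter rests wholly on assumed inputs. For a utility gain of 0.02-0.05, the estimated QALY difference is zero or negative in about 3-31% of trials with unadjusted QALYs and about 0-17% on change from baseline. The 95% interval for the QALY difference includes zero in about 55-92% and 5-84% of trials respectively. A sign change is therefore plausible, not established as likely. An interval on the ratio that mixes quadrants is a realistic outcome unless the utility effect is at the upper end of the range and baseline is accounted for.

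The primary ISI test, the sample size and data collection are unaffected. I rate this a free improvement, not a must-fix.

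**What to change.** Amend the cost-effectiveness text in Section 9.4.3 before the economic data are analysed by arm:

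1. Report the ICER as a point summary only when both differences are positive. Otherwise state the result in words: dominant, dominated, or cheaper with fewer QALYs.
2. Base the verdict and its uncertainty on incremental net monetary benefit at 50,000 and at 150,000 per QALY, giving the mean, the 95% bootstrap interval and an acceptability curve.
3. State that patients are resampled within arm, with each patient's cost and QALYs kept together.

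The cost is SAP wording. The same 1,000 bootstrap samples supply every quantity, and no new data are needed.

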9.4.4 SAFETY ANALYSES N/A

9.4.5 BASELINE DESCRIPTIVE STATISTICS

18 May 2022

Independent-sample t-tests and chi-square analyses will be used to examine baseline differences between the two treatment groups (Somryst vs. mEUC) in clinical and sociodemographic characteristics.

9.4.6 PLANNED INTERIM ANALYSES N/A.

9.4.7 SUB-GROUP ANALYSES

In secondary analyses, we will repeat the primary analyses stratified by age, gender, nativity status, number of medical comorbidities, socioeconomic status, employment status, language proficiency, psychological profile [depression, anxiety, stress scores. The results (point estimates and 95% confidence intervals) will be displayed in a Forest plot, where marked subgroup differences will be visually evident and used for hypothesis generation about whether one or more of these factors influences treatment response.

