9.2 SAMPLE SIZE DETERMINATION

Prior studies suggest that CBT-I yields approximately an 8-point reduction in the ISI, our primary measure of insomnia, with the standard deviation (SD) of post-intervention change scores being 4 to 5 points. Our expectation is that the improvement in patients assigned to the intervention condition (Somryst) will be 8 points or greater, and that those assigned to minimally enhanced usual care (mEUC) will exhibit a 5-point improvement. Typically, we expect the SD of change scores to increase for longer intervals (e.g., 6 or 12 months), and have therefore conservatively based our power calculations on a SD (change) of 6.0. Accordingly, randomization of 200 patients to Somryst versus mEUC (1-to-1 ratio) will provide 90% power to detect a differential reduction (post-intervention and 6-month follow-up) in ISI of 3 points or larger, using a 2-tailed Wald chi-square test of the appropriate contrast. This sample size estimate allows for up to 15% attrition, such that we have baseline data on all 200 patients (collected prior to randomization), but follow-up data on only 170.

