9.4.9 EXPLORATORY ANALYSES

We will also conduct an exploratory analysis of treatment effect modification by baseline comorbidity level, a sensitivity analysis in which those using sleep medications are excluded, and a test of whether there were any group differences in the initiation/use of sleep medications (prescribed or over the counter)

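### The subgroup section looks for effect modification by eye on a forest plot and never estimates the difference between strata or its uncertainty

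*Combined protocol and SAP*

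**What the plan says.** Section 9.4.7 plans, as secondary analyses, to repeat the primary analysis within strata. The headings are age, gender, nativity, comorbidity count, socioeconomic position, employment, language proficiency and psychological profile. The last lists depression, anxiety and stress scores, so the count is eight headings or ten factors.

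Stratum point estimates and 95% CIs go into a forest plot, where "marked subgroup differences will be visually evident and used for hypothesis generation". The section gives no treatment-by-factor term, no definition of a marked difference, no cut-points and no statement on multiplicity.

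The interaction contrasts in Section 9.4.2 are Group × Time only. Section 9.4.9 adds an "exploratory analysis of treatment effect modification by baseline comorbidity level" but does not say how it will be done.

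**The concern.** The section wants to learn whether any listed factor changes the response to treatment. The quantity that answers this is the difference between the stratum effects, with its standard error. Separate stratum analyses display the two effects and leave the comparison to the reader's eye.

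Two readers can apply different visual rules to the same plot, and these rules have very different error rates. Because the plan does not say what counts as marked, nobody can state in advance how often the screen will flag a factor that does nothing. What is at stake is the quality of the hypotheses carried forward: which patients a later study is designed around, and what the trial report suggests about who benefits.

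**Working it through.** **Inputs from the documents**
- Test: "Significance will be evaluated with a two-tailed p value of 0.05" (Section 9.4.2).
- Design: "randomization of 200 patients to Somryst versus mEUC (1-to-1 ratio) will provide 90% power to detect a differential reduction" in "ISI of 3 points or larger, using a 2-tailed Wald chi-square test" (Section 9.2).
- SD: the plan "conservatively based our power calculations on a SD (change) of 6.0" (Section 9.2). The same section gives 4 to 5 points for the SD of post-intervention change.
- Attrition: "This sample size estimate allows for up to 15% attrition", leaving "follow-up data on only 170", that is 85 per arm.

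**Assumptions, because the documents give no figures:** two levels per factor; a 50/50 split, with 30/70 and 20/80 as the range; arms balanced within strata; the same true effect in every patient. A simple comparison of change scores stands in for the mixed model.

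**The plan's own figure.** SE = 6 × √(2/85) = 0.920. Power = Φ(3/0.920 − 1.96) = 0.903. The stated 90% reproduces.

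**Difference between two strata when the effect is identical.** The SE of each stratum effect is 6 × √(2/n per arm in the stratum). The SE of the difference is √(SE_a² + SE_b²). The chance of a gap of 3 points or more is 2 × [1 − Φ(3/SE_diff)].

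| Split | n per arm in each stratum | SE_a, SE_b | SE_diff | Chance of a gap ≥ 3 points |
|---|---|---|---|---|
| 50/50 | 42.5, 42.5 | 1.30, 1.30 | 1.84 | 10.3% |
| 30/70 | 25.5, 59.5 | 1.68, 1.10 | 2.01 | 13.5% |
| 20/80 | 17, 68 | 2.06, 1.03 | 2.30 | 19.2% |

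**Dependence on the visual rule (50/50).** If marked means that the two 95% CIs do not overlap, the gap must exceed 2 × 1.96 × 1.30 = 5.10 points. The chance is 2 × [1 − Φ(5.10/1.84)] = 0.6%. If it means a gap as large as the planned main effect, the chance is 10%. The plan does not choose between these or any other rule.

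**Sensitivity (50/50).** With all 200 followed, SE_diff is 1.70 and the 10% becomes 7.7%. With 170 followed, SD 5 gives SE_diff = 1.84 × 5/6 = 1.53 and a 5% chance; SD 4 gives 1.84 × 4/6 = 1.23 and a 1.5% chance. The 10% therefore belongs to the plan's cautious SD.

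**What an interaction contrast would deliver (170 patients, SD 6).** Power for a true 3-point difference between strata is Φ(3/SE_diff − 1.96) + Φ(−3/SE_diff − 1.96): 37% at 50/50, 32% at 30/70 and 26% at 20/80. The difference detectable with 80% power is (1.96 + 0.84) × SE_diff: 5.2, 5.6 and 6.5 points. If tested at 0.05 without adjustment, the chance of at least one false positive is 1 − 0.95⁸ = 34% for eight independent factors and 1 − 0.95¹⁰ = 40% for ten.

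**The case against.** The plan already limits the use. These are secondary analyses for generating hypotheses, confidence intervals are shown, and nothing is called a test. This stands: no confirmatory claim depends on them, and a reader who infers that the primary type I error is affected would be wrong.

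For a two-level factor, a careful reader could also derive the difference and its SE from the two stratum results. That is true, but the plan does not ask anyone to do it, and it does not help with factors that are scores or have several levels.

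The interaction contrast does not reduce chance findings either. The 34–40% applies to ten or eight unadjusted interaction tests just as it would to a visual rule set at the same 5% threshold, and power for a 3-point difference is low. This also stands. The gain is a displayed estimate with its uncertainty and a known error rate.

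Two stronger readings are tempting, and the documents support neither:
- A reader might infer that strata will be compared by whether each is significant. With a uniform 3-point effect and a 50/50 split, each stratum has Φ(3/1.302 − 1.96) = 63.5% power, so exactly one would be significant in 2 × 0.635 × 0.365 = 46% of cases. Section 9.4.7 states no such rule; it shows estimates and intervals. Even under that rule, a split result would occur less than half the time for any one factor.
- A reader might infer from Section 9.4.9 that the plan already adopts an interaction model for comorbidity. The section names effect modification but no method, and a stratified analysis would fit its words.

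**Conclusion.** The point holds as a minor one. Section 9.4.7 asks whether factors modify the treatment effect, but its method leaves the between-stratum difference and its uncertainty unestimated. Section 9.4.2 does not fill the gap. Section 9.4.9 may do so for comorbidity, but its method is not stated.

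Under the plan's SD of 6 with 170 followed, an identical effect produces a stratum gap of 3 points or more in about 10% of cases per factor, rising to 19% with a 20/80 split. The figure is lower if the SD is nearer 4 or 5. The splits, the two-level coding, the count of eight or ten and the independence of the factors are all assumptions. Independence is doubtful for depression, anxiety and stress, so 34–40% is a guide to the scale of multiplicity and not a forecast.

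**What to change.** In Section 9.4.7, for each listed factor, fit one model with a Group × Time × factor term to all patients. Keep the factor continuous where it is measured that way, and prespecify cut-points for any strata shown in the plot. Keep the forest plot and print the interaction estimate with its 95% CI beside each factor.

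Add a short statement that gives the number of factors examined and labels the results exploratory. It should say that no multiplicity adjustment is made (34–40% chance of at least one false positive over eight to ten independent factors), and that power for a 3-point subgroup difference is about 37%, or 26–32% with unequal splits. State in Section 9.4.9 whether the comorbidity analysis uses the same model. Settle this before outcome data are compared by arm, so that cut-points and the meaning of a marked difference are not chosen afterwards.

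The cost is a few more model terms and a few sentences, with no new data. The downside is that the intervals will be wide and most factors will be inconclusive.

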9.4.8 TABULATION OF INDIVIDUAL PARTICIPANT DATA

Individual participant data will be listed by measure and time point.

9.4.9 EXPLORATORY ANALYSES

We will also conduct an exploratory analysis of treatment effect modification by baseline comorbidity level, a sensitivity analysis in which those using sleep medications are excluded, and a test of whether there were any group differences in the initiation/use of sleep medications (prescribed or over the counter)

10 SUPPORTING DOCUMENTATION AND OPERATIONAL CONSIDERATIONS

10.1 REGULATORY, ETHICAL, AND STUDY OVERSIGHT CONSIDERATIONS

18 May 2022

10.1.1 INFORMED CONSENT PROCESS

10.1.1.1 CONSENT/ASSENT AND OTHER INFORMATIONAL DOCUMENTS PROVIDED TO PARTICIPANTS

Consent forms describing in detail the study intervention, study procedures, and risks will be given to the participant and written documentation of informed consent will be completed prior to starting the study intervention.

